7.1.2.1 Frequency of tumor re-evaluation

Tumor evaluation is done through CT scan of the brain, thorax and upper abdomen (including adrenal glands) every 8 weeks.

The baseline imaging is done within 14 days from randomization and thereafter every 8 weeks.

For the patients in arm B that will switch their treatment based on the biological PD, the baseline imaging will be the most recent one (regularly done as per schedule) to the treatment start to osimertinib.

7.1.2.2 Date of progression

This is defined as the first day when the RECIST (version 1.1) criteria for PD are met. Refer to Ref. 33 as well as below (section 7.2.1) for further information on what constitutes early progression, assessment of progression of non-target disease, new lesions and usage of FDG-PET to diagnose progression.

7.1.3 Oligoprogression

This is defined as the first day when the RECIST (version 1.1) criteria for PD are met however the number of new lesions is up to 3 and amenable to local therapies (stereotactic radiotherapy or surgery).

7.1.4 Reporting of tumor response

All patients included in the study must be assessed for response to treatment, even if there is a major protocol treatment deviation or if they are ineligible, or not followed/re-evaluated. Each patient will be assigned one of the following categories: complete response, partial response, stable disease, progressive disease, early death or not evaluable.

Early death is defined as any death occurring before the first per protocol time point of tumor reevaluation.

Patients' response will be classified as "not evaluable" if insufficient data were collected to allow evaluation per these criteria.

7.2 Endpoints Definition

7.2.1 Progression Free Survival Rate at 18 months (PFSR-OSI-18)

The primary endpoint in this study is Progression Free Survival rate according to RECIST 1.1 "while receiving osimertinib" at 18 months (PFSR-OSI-18). This endpoint is evaluated in arm B and C. In arm A, the endpoint is assessed to simply provide a point estimate for PFSR-OSI-18 and the corresponding confidence interval.

The primary endpoint is defined as the proportion of patients at 18 months who are alive and did not experience an event for PFS-OSI according to the definition in section 7.2.2.

Practically, the time point of disease evaluation corresponding to the primary endpoint is 18 months after randomization. Therefore, disease evaluation at 18 months (\pm /- 14 days) is required for all patients who are still alive and without an event for PFS-OSI at the 18th month. Disease evaluation done within a window of \pm /- 2 weeks will be taken into account for the 18-month assessment.

Progression Free Survival rate according to RECIST 1.1 "while receiving osimertinib" at 18 months (PFSR-OSI-18) will be estimated using the Kaplan Meier technique in order to take into account possible failures of follow-up not due or related to the event of interest (progression or death).

7.2.2 PFS by RECIST 1.1 while receiving osimertinib (PFS-OSI)

This endpoint is evaluated in arm B and C. In arm A, the endpoint is assessed to simply provide a point estimate for median PFS-OSI and the corresponding confidence interval.

ARM A:

For patients in arm A, progression Free Survival "while receiving osimertinib" (PFS-OSI) is defined as the time interval between the date of randomization and the date of disease progression according to the RECIST criteria (version 1.1) or death whichever comes first (i.e. calculated as the difference between the two dates). This corresponds to the classical definition of PFS according to RECIST v1.1.

For each patient, the value for PFS-OSI will be used in the analysis regardless of whether or not intercurrent events occur such as protocol treatment discontinuation or further use of other anticancer therapies or use of concomitant medication etc... As a consequence, tumor re-evaluation should continue until the event of interest despite the occurrence of any intercurrent event.

Patients alive and free of progression prior to the analysis cut-off date are censored at the date of the last disease assessment before the cut-off date.

ARM B and C:

- For patients in arm B and C switching to osimertinib, progression Free Survival "while receiving osimertinib" (PFS-OSI) is defined as the time interval between the date of randomization and the date of disease progression or death "after switching to osimertinib" whichever comes first (i.e. calculated as the difference between the two dates), thus taking into account the influence of the switching strategy under investigation on the following treatment line.
 - The baseline to determine disease progression is the baseline at randomization. For patients in arm B and C switching to osimertinib, the nadir of the measurements to determine progression is defined as the nadir after switching to osimertinib. Disease progression is defined in section 7.1.2 and date of progression is defined in section 7.1.2.2.
- For patients in arm B and C who do not start osimertinib for any reason, PFS-OSI is defined as the time interval between the date of randomization and the date of disease progression according to the RECIST criteria (version 1.1) or death whichever comes first (i.e. calculated as the difference between the two dates). This corresponds to the classical definition of PFS according to RECIST v1.1.
 - For each patient, the value for PFS-OSI will be used in the analysis regardless of whether or not intercurrent events occur such as protocol treatment discontinuation or further use of other anticancer therapies or use of concomitant medication etc... **As a consequence, tumor re-evaluation should continue until the event of interest despite the occurrence of any intercurrent event.**

If neither event has been observed prior to the analysis cut-off date, then the patient is censored at the date of the last disease assessment before the cut-off date.

7.2.3 Proportion of patients receiving osimertinib based on the determination of cfDNA T790M mutation positive

The proportion of patients receiving osimertinib based on the determination of cfDNA T790M is the number of patients receiving at least 1 dose of osimertinib based on the determination of cfDNA T790M (positive mutation). This endpoint is only defined and applicable for Arm B.

7.2.4 Time to progression on osimertinib (TTP-OSI)

Time to progression on osimertinib is defined as the time interval between the date receiving osimertinib and the date of disease progression. Death is not counted as an event.

The baseline to determine disease progression is the baseline at randomization. For patients in arm B and C switching to osimertinib, the nadir of the measurements to determine progression is defined as the nadir after switching to osimertinib.

Disease progression is defined in section 7.1.2 and date of progression is defined in section 7.1.2.2. If the event has not been observed or if the patient dies before the analysis cut-off date, then the patient is censored at the date of the last disease assessment or the date of death prior the cut-off date. Patients not receiving osimertinib are excluded for this endpoint. The nature of this endpoint is different in Arm A (first line progression) from Arm B and C (second line progression).

7.2.5 PFS-2

In Arm A, PFS-2 is calculated as the time between randomization and the second PD by RECIST 1.1 or death, irrespective of treatment(s) received.

In Arm B and C, PFS-2 is calculated as the time between randomization and the second PD by RECIST 1.1 or death after switching to osimertinib, the first PD being PD by RECIST 1.1 or by positive cfDNA T790M status. For patients unable to start osimertinib, PFS-2 is calculated as the time between randomization and the second PD by RECIST 1.1 on any subsequent off protocol anticancer treatment line.

If no PFS-2 event has been observed prior to the analysis cut-off date, then the patient is censored at the date of the last disease assessment before the cut-off date.

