6.2.5 During Follow-up

After end of treatment, patients will be followed up every 8 weeks for:

- Any anti-cancer therapy administered after osimertinib. Response to new anti-cancer therapy will be collected if available;
- Survival status;
- Complementary examination will be performed according local physician standards.

If treatment was interrupted without any objective PD per RECIST 1.1 being identified, follow-up will also include, until objective disease progression per RECIST 1.1:

Contrast-enhanced CT scan of the brain, thorax and upper abdomen performed every 8 weeks. If a
patient is allergic to contrast adequate premedication as per local practice should be provided.
Should there be any further constraint, the EORTC Headquarters should be contacted as soon as
possible.

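### PFS-2 omits death for arm B and C patients who never start osimertinib, which biases the PFS-2 estimates upward within those two arms

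*Combined protocol and SAP*

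**What the plan says.** Section 7.2.5 contains three event rules.

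- Arm A: "the second PD by RECIST 1.1 or death, irrespective of treatment(s) received".
- Arms B and C, patients who switch: "the second PD by RECIST 1.1 or death after switching to osimertinib".
- Arms B and C, patients who do not switch: "For patients unable to start osimertinib, PFS-2 is calculated as the time between randomization and the second PD by RECIST 1.1". That progression must fall on a later line given off protocol, and death is not listed.

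One censoring rule covers all arms: "If no PFS-2 event has been observed prior to the analysis cut-off date, then the patient is censored". The censoring time is the most recent disease assessment up to the cut-off.

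Section 7.2.5 also lets the first progression in arms B and C be either a RECIST progression or a positive cfDNA T790M test.

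Follow-up imaging differs by arm. Section 6.1.4 has arm A scanned every 8 weeks until a second RECIST progression. Section 6.2.5 (arm B), with matching text in 6.3.5 (arm C), says: "If treatment was interrupted without any objective PD per RECIST 1.1 being identified, follow-up will also include, until objective disease progression per RECIST 1.1". Survival status is collected every 8 weeks after end of treatment in all arms.

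Section 8.2.2 plans Kaplan-Meier medians for PFS-2 and foresees comparisons between arms for BPFS only.

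**The concern.** The same death is treated differently by arm. A patient who dies before a second progression has an event in arm A. In arm B or C, a patient who dies on gefitinib, or after first progression without reaching osimertinib, is censored. How widely unable to start is read makes no difference: a death on gefitinib lies outside the rule for switchers, and the rule for non-starters does not count it either.

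Kaplan-Meier assumes that a censored patient has the same future risk as those still under observation. A patient censored at the last scan before death does not, so the curve is pushed up.

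At stake are the PFS-2 estimates for arms B and C and any side-by-side reading of them with arm A. Section 1.4 says the trial will examine upfront against sequential osimertinib, and section 8.1.1 says secondary endpoints should inform whether an arm is explored further.

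**Working it through.** **Is the omission repaired elsewhere?** The protocol summary and section 8.2 name PFS-2 but do not redefine it. Two neighbouring definitions are informative. Section 7.2.2 counts death for the same non-starters in PFS-OSI, and section 7.2.4 states outright that death is not an event for TTP-OSI. Section 7.2.5 does neither, so the text as written leaves death out.

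**Size.** The plan gives no expected PFS-2 rate, event count or non-starter rate, so there is no stated figure to reproduce. Two illustrations follow, both with exponential times and cut-off 24 to 50 months after entry (26 months of accrual plus 24 months of follow-up, section 8.1.1).

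*Illustration 1: 24 months, non-starters censored at first progression.*

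- Gefitinib median: 9 × ln 2 / (−ln 0.55) = 10.4 months, from the 55% PFS at 9 months in section 1.4.
- Osimertinib median: 9.7 months, the T790M-positive figure in section 1.3.
- Non-starters' median from first progression to second progression or death: 6 months (assumed).
- Non-starter rate: 5% to 30% (assumed).

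| Never start | Overstatement at 24 months, no second PD documented | Same, half documented | Shift in median, none documented |
|---|---|---|---|
| 5% | about 1.6 points | about 0.8 | – |
| 10% | 3.2 | 1.5 | 1.4 months |
| 20% | 6.4 | about 3 | 3.1 months |
| 30% | 10.3 | 4.7 | 5.0 months |

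*Illustration 2: 18 months, non-starters censored at the last 8-weekly scan before death.* Gefitinib median 12 months (section 1.2), osimertinib 10 months (9.7 rounded), non-starters' median time from randomization to death 6 to 12 months (assumed).

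| Never start | None documented | Half documented |
|---|---|---|
| 5% | 2.4–3.2 points | 1.3–1.6 |
| 10% | 5.0–6.5 | 2.4–3.1 |
| 20% | 10.1–13.2 | 4.8–6.2 |
| 30% | 15.4–20.0 | 7.2–9.0 |

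One cell can be checked by hand: 10% non-starters with median 9 months to death.

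- Hazards for switchers: λ1 = ln 2 / 12 = 0.05776 and λ2 = ln 2 / 10 = 0.06931.
- Switchers at 18 months: (λ2·e^(−18λ1) − λ1·e^(−18λ2)) / (λ2 − λ1) = (0.06931 × 0.3536 − 0.05776 × 0.2872) / 0.01155 = 0.685.
- All patients, death counted: 0.9 × 0.685 + 0.1 × 2^(−18/9) = 0.617 + 0.025 = 0.642.

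The simulation gives the same 64.2% with death counted. Under the current wording non-starters add time at risk but no events, so the curve must lie above the switchers' 68.5%. The simulated value is 69.9%, an overstatement of 5.7 points, and the median moves from 24.6 to 27.3 months.

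The bias was upward in all 24 scenarios of illustration 2.

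**Direction against arm A.** Arm A has no such censoring. Arm C switches on RECIST progression only (section 5.3), so nothing in the PFS-2 definition offsets the bias and arm C looks better against arm A. For an arm B patient who switched on a T790M result, the test counts as first progression and the first RECIST progression afterwards is already the PFS-2 event. That pulls arm B down, so the net direction is not determined.

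**The case against.** The strongest reply is that this is a drafting slip in a descriptive endpoint. The endpoint is a form of progression-free survival, arm A counts death, PFS-OSI counts death for these same patients, and the protocol says so where it means to exclude death. This is probably right about intent. It does not change what an analyst following section 7.2.5 would do.

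Five further points limit the concern, and they stand.

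- A reader might infer that both sequential arms are biased upward relative to arm A. The documents support this for arm C only, for the T790M reason above.
- A reader might infer that the upfront-versus-sequential conclusion rests on a PFS-2 test. None is planned: sections 8.2 and 8.2.2 analyse arms separately except for BPFS. The deaths in question do count in OS, and section 7.2.2 counts death for non-starters in PFS-OSI, on which the primary endpoint rests.
- A reader might infer that a second progression in non-starters will hardly ever be recorded. The documents do not say so. Scans are not required after first progression, but sections 6.2.5 and 6.3.5 collect later therapy, response to it where available, and local examinations. The none-documented columns are therefore an extreme case.
- The non-starter rate may be low, since B and C patients switch at RECIST progression whatever their T790M status. Non-starters may also include refusals and toxicity withdrawals, so they are not simply the worst patients. The 9.7-month osimertinib median applies to T790M-positive tumours, and section 1.3 gives 3 months for T790M-negative ones.
- With 49 patients per arm, the 95% half-width for a rate near 50% is 1.96 × √(0.25/49) = 14 points, larger than the bias in most scenarios. But a wide interval does not correct a biased estimate.

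**Conclusion.** The concern holds in a limited form. As written, section 7.2.5 censors deaths in arm B and C patients who never start osimertinib, and this biases Kaplan-Meier PFS-2 upward within those arms. The direction within each arm follows from the rule. The size is conditional on a non-starter rate that the documents do not give: at 24 months about 1.6 points for 5%, and about 3, 6 and 10 points for 10%, 20% and 30%, if no second progression is documented, and about half that if half are captured. Larger values arise if non-starters die early, as illustration 2 shows.

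The harm falls on descriptive estimates and on informal reading across arms. The documents do not support extending it to the primary endpoint, to a planned comparison, or to a settled A-versus-B bias. Correction is still worthwhile because the change is small and PFS-2 is a listed secondary endpoint measured from randomization in every arm.

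**What to change.** In section 7.2.5, use one definition for all arms: PFS-2 runs from randomization to the second progression or death from any cause, whichever comes first, whether or not osimertinib was started. For non-starters whose second progression was not imaged, take the date of death from survival follow-up as the event.

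The cost is one clause and the matching change in the analysis program. Survival status is already collected every 8 weeks, so no visits or scans are added. PFS-2 in arms B and C will fall by whatever the current rule adds.

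A limitation remains and should be stated. Scans after end of treatment are required only until first objective progression in arms B and C (6.2.5, 6.3.5) but to second progression in arm A (6.1.4). An un-imaged second progression in a B or C non-starter will be dated at death, so PFS-2 may still be somewhat long in those arms. A reader might infer that counting death puts all three arms on the same scale. It does not, because the imaging difference would remain.

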7.2.6 Overall Response Rate (ORR) to osimertinib

Overall Response Rate (ORR) to osimertinib is an overall rate including patients with documented complete response (CR) or partial response (PR) while patients are receiving osimertinib, where CR and PR are defined according to the principles mentioned in section 7.1.2. Patients not receiving osimertinib will not be included in the ORR to osimertinib analysis.

The nature of this endpoint is different in Arm A (first line ORR) from Arm B and C (second line ORR).

7.2.7 Treatment duration

Treatment duration will be measured from the time of randomization until the protocol treatment stops. In Arms B and C, if patients receive osimertinib, the duration is calculated till osimertinib stops.

7.2.8 Overall Survival (OS)

Overall survival (OS) is defined as the time interval between the date of randomization and the date of death from any cause. Patients still alive at the analysis cut-off date are censored at the last date known to be alive (before the cut-off date).

7.2.9 Brain progression free survival (BPFS)

Brain progression free survival is defined as the time interval between the randomization and the date of brain progression (progression within target lesions in the brain, unequivocal progression in non-target lesions in the brain, or appearance of new lesions in the brain) or death whichever comes first.

Disease progression is defined in section 7.1.2 and date of progression is defined in section 7.1.2.2. CT scan will be used to evaluate new or recurrence progression in the brain. If the event has not been observed or if the patient dies or has PD that hampered further assessment/evaluation of brain progression, then the patient is censored at the date of the last follow up examination or day of death.

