6.1.4 During Follow-up

After end of treatment, patients will be followed up every 8 weeks for:

- Any anti-cancer therapy administered after osimertinib. Response to new anti-cancer therapy will be collected if available;
- Survival status:
- Complementary examination will be performed according local physician standards.
- Contrast-enhanced CT scan of the thorax and upper abdomen and brain CT scan should be performed
 every 8 weeks until a second progression as per RECIST 1.1. If a patient is allergic to contrast
 adequate premedication as per local practice should be provided. Should there be any further
 constraint, the EORTC Headquarters should be contacted as soon as possible.

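### BPFS is censored at an undefined follow-up date that is not tied to brain CT, so unscanned time counts as brain-progression-free in every arm and can modestly bias A vs B and A vs C

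*Combined protocol and SAP*

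**What the plan says.** Section 7.2.9 defines BPFS as time from randomization to brain progression "or death whichever comes first". It names the assessment tool: "CT scan will be used to evaluate new or recurrence progression in the brain". Its last sentence deals with patients who have no event, and also applies "if the patient dies or has PD that hampered further assessment/evaluation of brain progression". For all of these, "then the patient is censored at the date of the last follow up examination or day of death".

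The neighbouring progression endpoints use a different date. In Section 7.2.2, living progression-free arm A patients "are censored at the date of the last disease assessment before the cut-off date", and arms B and C have the same rule. Sections 7.2.4 (TTP-OSI) and 7.2.5 (PFS-2) also use the last disease assessment for living event-free patients. Section 7.2.8 (OS) uses the last date known alive.

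The follow-up sections fix when brain CT ends. In arm A (6.1.4) it continues after treatment "every 8 weeks until a second progression as per RECIST 1.1". In arms B and C (6.2.5, 6.3.5) CT after treatment is conditional: "If treatment was interrupted without any objective PD per RECIST 1.1 being identified, follow-up will also include" 8-weekly CT, and only until objective progression. In all arms, 8-weekly follow-up for later therapy and survival continues after treatment ends, with no stated end at progression.

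Section 8.1.2 plans formal comparisons of A vs B and A vs C on BPFS.

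**The concern.** Brain progression is assessed by CT, so follow-up time without brain imaging carries little information about it. If the censoring date can be a survival or therapy contact, a patient last scanned at month 12 and contacted at month 30 contributes 18 months at risk with no opportunity for brain progression to be seen on a scheduled scan. The Kaplan-Meier curve is then too high. If unscanned time differs between arms, the hazard ratio is distorted too.

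BPFS is the only time-to-event endpoint for which Section 8.2 plans comparisons between arms, and its stated power is only about 70%. A distortion against arm A would use up power that the trial can hardly spare.

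**Working it through.** **1. The plan's own figure.** Section 8.1.2 gives 75% vs 87.5% at 18 months, HR 0.46, 36 events, one-sided 5% and about 70% power.

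- HR = ln(0.875)/ln(0.75) = 0.464.
- Freedman power: z = √36 × (1 − 0.464)/(1 + 0.464) − 1.645 = 0.55, so power is 70.9% (71.7% with HR 0.46).

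The stated figure is reproduced, and the censoring date does not enter the formula.

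**2. When the events occur.** With 52 patients per arm, 52 × (0.25 + 0.125) = 19.5 events fall by month 18. Exponential times, 26 months of uniform accrual and 24 further months give 23.0 + 12.4 = 35.4 events. So (35.4 − 19.5)/35.4, about 45%, come after month 18, when stopped scanning matters most.

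**3. When scheduled brain CT ends.**

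| Patients | CT ends at | Source |
|---|---|---|
| Arm A | second RECIST progression, once osimertinib has stopped | 6.1.2.4, 6.1.4 |
| B/C switched at RECIST progression | progression on osimertinib, normally the second RECIST progression | 6.2.2.2, 6.3.2.2, 6.2.5, 6.3.5 |
| Arm B switched on cfDNA T790M | progression on osimertinib, which may be the first RECIST progression | 5.3, 6.2.5 |
| B/C never starting osimertinib | first RECIST progression | 6.2.5, 6.3.5 |

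Every arm therefore has unscanned time. The arms differ mainly through the last two rows. Since protocol version 4.0, arm B patients still on gefitinib switch only on RECIST progression (Section 4), so the third row covers patients switched before that.

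**4. Illustrative effect on the hazard ratio.** The documents give no brain-progression or death rates after progression, so these inputs are assumptions:

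- 100,000 simulated patients per arm, 8-weekly scans, and the plan's accrual and follow-up.
- Progression times anchored on Sections 1.2 and 1.3 (medians of 12, 9.7 and 5.4 months; 12-month PFS of 71.7%).
- Brain hazard 0.010 per month in both arms, constant or doubled after first progression.
- Death hazard 0.004 per month before second progression; median 10 months from second progression to death.

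The true HR (A relative to B/C) is 1.00. Columns give the share of B/C patients whose CT ends at the first RECIST progression.

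| Rule | 0% | 20% | 50% | 100% |
|---|---|---|---|---|
| Last follow-up, death an event | 1.00 | 1.03-1.05 | 1.05-1.12 | 1.13-1.24 |
| Last follow-up, death censored | 0.99 | 1.08-1.14 | 1.25-1.40 | 1.68-2.21 |
| Last brain CT, every death an event | 1.00 | 0.97-0.99 | 0.91-0.96 | 0.83-0.91 |
| Last brain CT, death censored | 0.99-1.00 | 0.99-1.03 | 0.99-1.09 | 0.98-1.27 |

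A second simulation with a share of 20-50% gave, in the same row order, 1.02-1.10, 1.07-1.33, 0.93-0.99 and 0.99-1.08.

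With a real brain effect (hazards 0.0046 vs 0.010) and a share of 0%, mean unscanned time was about 5.4 months in A and 6.5 in B/C. The current date then gave HR 0.69 against a true 0.68, and 0.65 against 0.62, with death an event. With death censored it gave 0.48 against 0.45, and 0.42 against 0.40.

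**5. What this does to the test.** With 36 events, SE(log HR) is about 2/√36 = 0.333.

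- Current date, death an event: an apparent null HR of 1.02-1.12 is a shift of ln(1.02)/0.333 = 0.06 to ln(1.12)/0.333 = 0.34 SE. One-sided 5% error falls to 4.4%-2.4%.
- Last brain CT with every death counted: 0.99-0.91 is a shift of −0.03 to −0.28 SE. The error rises to 5.3%-8.7%.

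**6. The death rule.** In the effect scenario (share 0%, constant brain hazard), the two arms give 26.3 + 32.8 = 59.1 events if death counts and 5.4 + 10.1 = 15.5 if it is censored. The contradiction in 7.2.9 thus also decides whether 36 events are within reach.

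**The case against.** The examination in 7.2.9 may mean an imaging examination. The sentence follows the one naming CT, and its clause on progression that prevents brain assessment would have little purpose if such patients were carried to later contacts. OS has its own wording for last contact. This reading is possible, but it is not stated. The protocol's follow-up sections describe contacts that need not include CT, so the ambiguity stands.

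A reader might infer that unscanned time builds up only in arms B and C, and that the formal comparisons are therefore biased. The documents do not support this. Arm A also stops CT at second progression while contacts continue. In B and C scanning continues through gefitinib progression and the switch. With equal disease courses and no B/C patient stopping at first progression, the null HR is about 1.00.

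With death as an event, the distortion is a fraction of one standard error and works against arm A, so it costs power rather than creating false claims. That is fair. It is also fair that moving the censoring date alone, with all later deaths counted, can turn the bias in favour of A by about as much. Finally, local examinations under 6.2.5 and 6.3.5 may pick up some brain progression after scheduled CT ends. This would reduce the effect by an unknown amount.

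**Conclusion.** The textual defect is firm: 7.2.9 does not tie the BPFS censoring date to brain imaging, unlike the related endpoints, and it treats death as both an event and a censoring reason. Read literally, it overstates BPFS in all arms.

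Bias in A vs B and A vs C is possible, not shown. It is probably modest and against arm A. If 20-50% of B/C patients stop CT after one RECIST progression, a null HR of 1.00 appears as roughly 1.02-1.12 with deaths as events and 1.07-1.40 with deaths censored. That share, and the hazards after progression, are assumptions. The larger values arise only if deaths are censored, so the death rule matters more than the censoring date. The point should be settled before the BPFS analysis.

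**What to change.** Make three changes to 7.2.9 in one amendment:

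1. Censor patients alive without brain progression at the last evaluable brain CT before the cut-off.
2. State once whether death is an event or a censoring reason, and delete the conflicting wording.
3. State how deaths after brain CT has stopped are handled. Counting all of them while censoring unscanned survivors early can reverse the bias.

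Report the version censored at last follow-up, and the alternative handling of late deaths, as sensitivity analyses.

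The drafting cost is small, and scan tracking already exists (15.4.1). The price is less BPFS follow-up time, somewhat lower estimates and some residual bias in either direction. For example, counting only deaths within two scan intervals of the last scan, in the effect scenario with constant brain hazard, gave HR 0.625 against a true 0.675 when no B/C patient stopped CT early, and 0.734 against 0.683 when all did. No rule for late deaths is free of assumptions, which is why the alternatives should be reported.
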